## 8.0 DEVICE INFORMATION

All the investigational devices required in the PRAMA protocol to perform the TMA procedure are 510(k)-cleared and used in accordance with their respective indications for use, as described below:

- Based on the 510(k) of AveCure™ Ablation System (reference: K143203):  
*"The MedWaves AveCure™ Ablation System is intended for use in percutaneous, laparoscopic, and intraoperative coagulation-ablation of soft tissue. The MedWaves AveCure™ Ablation System is not intended for use in cardiac procedures."*
- Based on the 510(k) of TRINITY / 3D PROSTATE SUITE (reference: K170521):  
*"TRINITY and its embedded 3D PROSTATE SUITE software are intended to be used by clinicians and their assistants, qualified to perform ultrasound diagnosis and ultrasound-guided procedures, in public or private hospitals. TRINITY is indicated to:*
  - *Generate ultrasound images for structural analysis and fluid flow analysis for*
    - *Urology,*
    - *Gynecology,*
    - *Vascular,*
    - *Abdominal,*
    - *Small organs,*
    - *Soft tissues and*
    - *Musculoskeletal exams*

---

*TRINITY is not indicated for ophthalmic and cranial ultrasonography.”*

To summarize, the TMA procedure will be performed on soft tissue (prostate). The ablation will be achieved thanks to MedWaves AveCureTM Ablation System under ultrasound-guidance using TRINITY. Besides, the risks associated with this procedure are known, controlled and well-described, as previously outlined, qualifying the procedure as a non-significant risk procedure.

## **9.0 CORRELATIVES/SPECIAL STUDIES**

### **9.1. Correlation of histology with MRI**

Following prostatectomy, the prostates will primarily be evaluated using standard-of-care diagnostic methods, and secondarily be assessed in accordance with the thermal treatment parameters. The intact prostate specimens should be received in pathology within two up to six hours of prostatectomy. Standard gross examination of prostate specimens will be done including measurement, appropriate inking for margins and serial transverse sectioning from the bladder neck across the prostate to the penile urethral margin. Digitally photographing of these sections will be done. TTC viability staining will be performed not less than 2 hours after TMA and 4 up to 6 hours after completion of prostatectomy. Macroscopic evaluation of the TTC stained sections will be performed where viable tissues would exhibit maroon color change, while ablated non-viable tissues should show absence of color change. Routine tissue processing and H&E staining will be performed. H&E stained whole mount sections of the prostatectomy specimens will be evaluated on microscopy. If indicated, IHC staining will be done.

## **10.0 STATISTICAL CONSIDERATIONS**

All patients who sign the consent and are registered will be accounted for. However only those patients who undergo TMA and who undergo the radical prostatectomy will be included in the primary analyses; these will be the fully evaluable patients. Those who fail to complete the protocol as planned will be summarized; reasons for failure to complete will be examined.

### **10.1 Summary of Design**

This is a feasibility study to evaluate whether TMA is promising as a stand-alone local treatment for men with localized prostate cancer, thereby eliminating the need for prostatectomy or standard radiation as the primary treatment. For practical considerations, the total number of study participants is limited to 15 patients by 1) cost and 2) feasibility (could not do many more during the funding

---

period). The number of patients included may be extended considering the need to evaluate different treatment parameters (still according to manufacturer data).

#### **10.2 Justification of Trial Design.**

- The decision to evaluate at 5 patients in immediate resection phase would provide intraoperative safety and feasibility, and evaluation of the ablated area on the radical prostatectomy specimen assessed by TCC stanning according to TMA delivery protocols. The decision to evaluate at 10 patients in delayed resection phase would provide intraoperative safety and feasibility, in addition to estimate of the short-term safety after TMA, evaluation for functional status (urinary symptoms, potency, incontinence), PSA response, MRI evaluation, prostate biopsy evaluation, safety and feasibility of salvage prostatectomy after TMA, and evaluate tissue viability on HE stanning. Additionally, The post-TMA MRI and prostate biopsy performed just prior to the delayed radical prostatectomy will be used to predict/evaluate the actual prostatectomy findings.

#### **10.3 Primary Objective Statistical Considerations**

To determine the feasibility of transperineal targeted microwave ablation of an MRI-identified index prostate tumor in patients undergoing radical prostatectomy, we will evaluate the viable tissue remaining after TMA using histologic examination of excised prostate specimen.

#### **10.4 Secondary Objective Statistical Considerations**

The intra-operative safety of the targeted microwave ablation, the number of microwave ablations needed to ablate one mpMRI-visible lesion, the ease of use of the operative procedure and the feasibility of the immediate or 1 mo delayed radical prostatectomy after the targeted microwave ablation will also be evaluated.

#### **10.5 Descriptive Objective Statistical Considerations**

NA

#### **10.6 Sample Size and Patient Accrual**

Due to the nature of exploratory and feasibility study design, the sample size of 15 subjects was determined by practical considerations, including cost and feasibility (could not do many more during the funding period).

Through the immediate resection phase, 5 practical TMA templates and their ablation areas are evaluated. With following the delayed resection phase, the short-term safety and feasibility of TMA templates are evaluated.

The number of patients included may be extended considering the need to evaluate different treatment parameters (still according to manufacturer data).

---

## 10.7 Data Analyses Plans

All patients who sign the consent form will be registered and entered the database. For each patient, we will list whether he received the assigned protocol (and if not, the reasons), the outcome of the procedures, compliance with the protocol (and reasons for failure to comply), adverse events with any of the procedures, MRI results, and targeted biopsy results.

- The data from the immediate resection phase and delayed resection phase will be separately evaluated. The observed ablated area in immediate resected prostatectomy specimen based on TTC staining will be compared with the predicted ablation area according to the template. The tissue viability will be evaluated by HE staining on delayed resection prostatectomy specimen.
- The comparison of the difference between the treatment effect dimensions measured histologically on the prostatectomy specimen resected after TMA and the predictive ablation charts provided by the manufacturer will be performed. For this analysis, the data from immediate resection phase and delayed resection phase are separately evaluated.
- The comparison between the treatment effect dimensions measured histologically on the prostatectomy specimen resected one month after TMA, compared to post TMA dimensions measured on the pre-RP mpMRI.
- To evaluate the intra/post-operative safety of TMA, we defined 30% as clinically acceptable severe adverse events (defined as CDC  $\geq 3$ ) rate. If the severe adverse events occur less than 30% (equivalent to less than 4 cases in 10 cases) for the delayed ablation phase, the feasibility of TMA is proved.

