**E) RP + pelvic node dissection**

### HISTOLOGICAL CORRELATION (Whole-mount step-sectioned RP specimen) with

- F) Predictive ablation charts** of the manufacturer, providing estimations of necrosis dimensions for different input power, time and energy
- G) Localization of the predicted ablation** after 3D reconstruction of the prostate (“3D map”) on the KOELIS Trinity® system
- H) Imaging** correlates with post TMA MRI

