Diagnosis and Main Inclusion Criteria	
 
• Male
 
• Index lesion visible on multiparametric MRI confirmed by targeted transperineal biopsies using KOELIS Trinity®
 
• Having a diagnosis of prostate cancer (Gleason score ≤8)
 
• Prostate size ≤ 150 cc
 
• Patient suitable for IV sedation or general anesthesia and focal targeted microwave ablation
 
• Having elected to undergo RP as treatment of choice
 
• Ability to understand and the willingness to sign a written informed consent
 
• Free, informed, and written consent, dated and signed before the enrollment and before any exam required by the trial
 

Study Product(s), Dose, Route, Regimen	A TMA ablation will be performed during each intervention.
Duration of administration	NA
Reference therapy	NA
Statistical Methodology	
For practical considerations, the expected total number of study participants is 15 patients. This number may be extended in case further ablation parameters need to be tested.
 
An analysis is planned to determine TMA delivery protocol (number of ablations, energy output, and time needed to ablate one MRI-visible lesion).
 
We will assess the correlation between the treatment effect dimensions measured histologically on the prostatectomy specimen resected immediately or 1mo after targeted microwave ablation, compared to the predictive ablation charts provided by the manufacturer.
 
We will report the ablated area on the radical prostatectomy specimen assessed by viability tissue staining (TTC) on all fully evaluable patients.

---

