## **2.2 Secondary Objectives**

- KOELIS Trinity ability to plan and guide treatment needles and ablations in the prostate index lesion
- Impact of treatments on functional outcomes and quality of life
- Predictability of Medwaves Avecure microwave ablation charts
- Predictability of post microwave ablation mpMRI

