## **2.4 Primary Endpoints**

The ablated area on the radical prostatectomy specimen assessed by viability tissue staining (TTC).

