#### **Template #5**

In order to avoid collateral damage and for safety, the TMA delivery protocol may be modified by the physician's discretion but still in accordance with the manufacturer's recommendation.

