### 5.3.3 TMA

**TMA preparation:** The patients are instructed to self-apply rectal 2 enemas: one the night before, one the morning of TMA; nothing per oral night prior (8hs) to TMA.

**Patient position and probe position:** The patient is brought into the operating room and general anesthesia is obtained. Prophylactic antibiotic (Levaquin 500mg IV) is administered. The patient is placed in lithotomy position. The genitalia and perineal are prepped and draped in a sterile fashion. Digital rectal exam is performed. The 3D Side Fire endocavity TRUS probe (K3DEL00, Koelis, Meylan, France) is then inserted into the rectum.

**Ablation planning:** The prostate is TRUS-scanned, the transverse and longitudinal images are acquired, the dimensions of the prostate are measured and the 3D volume of the prostate is acquired. The ultrasound (US) images are adjusted to provide optimal visualization of the prostate, rectal wall and surrounding tissues. The contours of the prostate are drawn to delineate the prostate contour, the urethra contour, the rectal wall contour. After fusion with the preoperative MRI, the ablation zones set by the manufacturer can be visualized in 3D as a simulation prior to the needle insertion.

**TMA delivery and monitoring:** Under real-time TRUS guidance, a microwave antenna is transperineally inserted into the planned-ablation area. As much as possible, the needle will be placed at the center of the index tumor to maximize the treatment effect inside the lesion. OBT-Fusion® guidance ensures the proper location of the needle with respect to the targeted index lesion. Once the needle location is confirmed and the optimal treatment parameters are chosen, the microwave generator is configured accordingly, and the treatment can start. The ablation typically lasts for a few minutes.

**Post-treatment:** After the procedure, the antenna and TRUS probe are withdrawn and the robotic RP as standard of care for the prostate cancer starts under same general anesthesia. Patients is sent to the recovery room for monitoring. After completely recovery from the anesthesia the patient stays hospital overnight or is discharged home with the urethral Foley in place. Prescriptions are provided for: bladder antispasmodic, anti-inflammatory, and antibiotics.

---

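### Section 10.7 compares the TTC ablated area with the size predicted by the assigned template, even where the physician has modified the ablation as section 4.2 allows

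*Combined protocol and SAP*

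**What the plan says.** The first bullet of section 10.7 treats the two phases separately. In the immediate resection phase the area seen on TTC staining "will be compared with the predicted ablation area according to the template". In the delayed phase that bullet asks only for tissue viability on HE staining. The second bullet compares histological dimensions with the manufacturer's charts, again by phase. It names neither the template nor any setting at which the charts are to be read.

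The study schema describes the charts as "providing estimations of necrosis dimensions for different input power, time and energy". Section 2.2 lists "Predictability of Medwaves Avecure microwave ablation charts" as a secondary objective.

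Section 4.2 gives the manufacturer's short and long axes for three ablation times and assigns one of five templates to each man. It then adds: "In order to avoid collateral damage and for safety, the TMA delivery protocol may be modified". The decision is the physician's and must stay within the manufacturer's recommendation. Section 5.3.3 describes the procedure itself: "Once the needle location is confirmed and the optimal treatment parameters are chosen, the microwave generator is configured accordingly".

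On departures, section 10.7 says for each patient: "we will list whether he received the assigned protocol (and if not, the reasons". It also has ablation time recorded. The synopsis plans an analysis of the delivery protocol that covers "number of ablations, energy output, and time needed to ablate one MRI-visible lesion".

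**The concern.** The comparator in the first bullet is fixed by the plan for the man, while the tissue effect is fixed by what he received. Section 4.2 allows these to differ without any protocol breach. When they do, the gap between observed and predicted area has two sources: error in the chart, and the change in dose. The comparison as written does not separate them.

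At stake is what the study says about how well the charts predict prostate tissue destruction. The charts come from other soft tissues, so this is one of the more useful things the study can report. An accurate chart could look as if it over-predicts because an ablation was shortened for safety. Listing the man as not having received the assigned protocol flags the case, but it leaves the comparator as it was.

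**Working it through.** The plan states no figure for this comparison, so there is none to reproduce. The check sizes the effect from the plan's own predicted dimensions.

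**Inputs**

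- Predicted short x long axis in section 4.2: 1.5 x 2.5 cm (3 min), 2.0 x 2.7 cm (5 min), 2.5 x 3.0 cm (long). The long size is taken as the 7.5 min of Template #3.
- Ablations per man in section 4.2: template 1, two; template 2, two; template 3, one; template 4, two; template 5, two. The immediate phase has one man per template.
- Assumption: a modification is a cut to a shorter listed time. Section 4.2 grants the discretion to avoid damage, so a cut is the natural direction, but the documents do not say how delivery would change. A longer time would shift the comparison the other way.
- Assumption: the ablated zone is an ellipse in the plane of its long axis.

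**Predicted areas** (area = π/4 x short x long)

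- 3 min: π/4 x 1.5 x 2.5 = 2.945 cm²
- 5 min: π/4 x 2.0 x 2.7 = 4.241 cm²
- 7.5 min: π/4 x 2.5 x 3.0 = 5.890 cm²

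**Apparent shortfall if the chart is exactly right** (1 - area at delivered time / area at template time)

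| Template time | Delivered time | Calculation | Shortfall against template |
|---|---|---|---|
| 5 min | 3 min | 1 - 2.945/4.241 | 31% |
| 7.5 min | 5 min | 1 - 4.241/5.890 | 28% |
| 7.5 min | 3 min | 1 - 2.945/5.890 | 50% |

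Read at the delivered time, the shortfall is 0% in each row.

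**Sensitivity to the shape assumption.** Section 5.3.4 sections the prostate transversely. If the area were read at right angles to the antenna, as a circle on the short axis, the shortfalls would be 1 - 1.5²/2.0² = 44%, 1 - 2.0²/2.5² = 36% and 1 - 1.5²/2.5² = 64%.

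**Reach.** The immediate phase plans 2 + 2 + 1 + 2 + 2 = 9 ablations. The figures apply to templates 2 and 3, which is 2 + 1 = 3 of the 9, in two men. Template 1 already uses the shortest listed time. Section 4.2 gives no predicted size for the overlapped ablations of templates 4 and 5, so a change there cannot be sized. The appendix on delivery strategy is only a heading in the text available, and it may hold more.

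**The case against.** The strongest reply is that a template comparator suits the first bullet. Section 10.6 says the immediate phase evaluates five templates and their ablation areas, so planned against observed is a fair question. The second bullet serves the chart objective, and because the charts are indexed by power, time and energy, the natural way to look up an ablation is at the settings applied. The study is a 15-man exploratory one with no test or success threshold on this comparison, and a modified man would be visible in the listing. All of this stands, and it keeps the point small. It does not remove it: the first bullet states a comparator, and for a modified ablation that comparator is the prediction for another dose.

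Three stronger readings are tempting, and the documents do not support them.

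- *The delayed phase is affected as well.* Templates 2 and 3 account for 2 x 3 = 6 of its 2 x 9 = 18 ablations. But the template comparator is stated only for TTC specimens from immediate resection, and the second bullet does not name the template.
- *With one man per template, chart error and dose change cannot be told apart.* Section 10.7 has ablation time recorded, so for a change in time the recorded minutes and the sizes in 4.2 separate the two without a second man. Template 2 also gives two ablations in its one man, and one of them may stay at plan. The gap is that the plan does not call for this step. Delivered power and energy are not named there as recorded, though that does not show that the case report form lacks them.
- *Section 5.3.3 shows that settings are routinely chosen away from the template.* Its wording may only mean configuring the generator for the assigned template. The modification clause in 4.2 is what clearly permits a departure.

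**Conclusion.** The point holds, and it is minor. In the immediate resection phase the stated comparator for a modified ablation is the predicted size for a dose that was not given. Under the assumptions of elliptical zones and a cut to a shorter listed time, a perfectly accurate chart would appear to over-predict, with observed area 28% to 50% below the template value. That applies to at most 3 of the 9 planned TTC-phase ablations, in two men.

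The documents do not say how often delivery will be modified, and it may be never. A reader might infer that the primary endpoint is compromised. It is not: that endpoint is the ablated area itself, which does not depend on any prediction. Wherever the template is followed, the comparison is sound as written. The second bullet needs only matching wording, so that both comparisons read the charts in the same way.

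**What to change.** In section 10.7, first bullet, make the main comparison with the chart size at the settings actually delivered, and show the template prediction beside it. Flag each modified ablation with its reason. Put the same wording in the second bullet for consistency. Use the ablation time that 10.7 already records, and confirm that delivered power and energy are also captured for each ablation. The templates fix time but not power, and the synopsis already plans to look at energy output. Because any modification must stay within the manufacturer's recommendation, a chart value should normally exist for the delivered setting.

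The cost is about two sentences in 10.7 and a check of the case report form. Nothing changes for patients, and the physician's freedom to modify delivery for safety stays as written. The one drawback is that a template with a modified man has fewer ablations to report at its planned setting. Setting the rule now also avoids choosing the comparator after the specimens have been seen.

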Definitive data attesting to the precision of TMA at the Pca tissue level are critical, as well as data documenting the most adequate treatment parameters to achieve such precision. Such fundamental, prostate tissue-level data in the human are lacking. To date, no published human studies have reported spatial thoroughness of TMA prostate tissue kill as correlated with contemporary imaging and histology to assess and predict tissue destruction; nor have TMA technologic parameters been directly correlated with thoroughness of human prostate tissue kill.

The critical barrier to solve this problem is the ability to thoroughly examine the whole prostate gland in relatively close proximity to TMA ablation, timed appropriately to measure the relevant changes induced. Analyses should be soon enough before the ablated tissue starts to undergo fibrotic atrophy and shrinkage, as these would invalidate accurate comparison between imaging versus histologic measurements (e.g. salvage RP many months after TMA would not accomplish this, and it would also result in worse clinical outcomes for the patient due to peri-prostatic scarring involving the neurovascular bundles and sphincter).

A Method, named as Triphenyltetrazolium chloride (TTC) staining, for assessing lethal thermal tissue injury is available which rely on the functional status of cellular enzymes and mitochondrial energy production to produce differential staining between thermal tissue necrosis and adjacent untreated viable tissue. The dehydrogenase enzymes assessed by this staining method are essentially within the mitochondria and utilize NADH/NADPH as electron donors to promote redox reactions. This viability stains use members of the tetrazolium family as their chromogen (stain colorant). The dehydrogenase enzymes and their cofactors (NADH and NADPH) reduce the colorless tetrazolium molecule into a colored formazan pigment (viable tissue). Following a thermal treatment, tissues with resultant denatured cellular enzymes and/or disrupted mitochondrial cofactor production will be unable to convert tetrazolium to its colored form and remain their native color (non-viable tissue) [34]. We adapt TTC staining to assess the location and extent of a treatment's ablation/thermal effect within the prostate. The use of TTC staining does not limit subsequent histologic prostate evaluation which is essential for optimal patient standard of care.

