When performing and evaluating viability stains, timing of the staining procedure is important. On the other hand, TTC staining should not be performed less than 2 hours from completion of the hyperthermic ablation. This post-treatment period allows for any residual enzyme and cofactor activity to fully cease and limits the risk of false positive staining. Thus, TTC staining should be performed more than 2 hours following the ablation and within 6 hours from tissue excision from the patient. This strict time frame is a rationale of the current ablation and immediate resect study protocol.

In order to evaluate the feasibility of TMA in more practical setting, further analyses should be delayed long enough post-TMA treatment to allow tissue changes of irreversible thermal damage to set in. In this setting, we evaluate the ablation effect on histology using HE staining instead of TTC staining. This delayed resection allows us to evaluate short term safety of TMA and predictivity of post ablation mpMRI. It may also allow us to identify potential histological elements occurring after TMA, such as fibrosis or scar tissue.

In this way, we will safely evaluate the optimal TMA protocol based on the first 5 cases, and will evaluate the practical feasibility of TMA using the following 10 cases.

We do not anticipate pre-surgical TMA will cause any significant technical difficulties during the performance of RP. Ablate and early resect studies have been performed after focal prostate ablation (HIFU, electroporation) with no reporting of adverse patient outcomes [35],[36]. Additionally, salvage (delayed) radical prostatectomy, years after failure of whole gland ablation, which are arguably much more challenging, is not an uncommon procedure offered at many centers [37],[38]. In fact here at USC, we have safely performed many (>100) salvage prostatectomies.

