### 5.3.4 Pathologic Evaluation

Following prostatectomy, the prostates will primarily be evaluated using standard-of-care diagnostic methods, and secondarily be assessed in accordance with the thermal treatment parameters. The intact prostate specimens should be received in pathology within two up to six hours of prostatectomy. Standard gross examination of prostate specimens will be done including measurement, appropriate inking for margins and serial transverse sectioning from the bladder neck across the prostate to the penile urethral margin. Digitally photographing of these sections will be done. TTC viability staining will be performed not less than 2 hours after TMA and 4 up to 6 hours after completion of prostatectomy. Macroscopic evaluation of the TTC stained sections will be performed where viable tissues would exhibit maroon color change, while ablated non-viable tissues should show absence of color change. Routine tissue processing and H&E staining will be performed. H&E stained whole mount sections of the prostatectomy specimens will be evaluated on microscopy. If indicated, IHC staining will be done.

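### Delayed-phase ablation dimensions read on processed H&E sections are compared with MRI and manufacturer charts without any correction for processing shrinkage

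*Combined protocol and SAP*

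**What the plan says.** Section 10.7 sets up two size comparisons that use the delayed-resection specimens. The first is with the MRI done before prostatectomy: "The comparison between the treatment effect dimensions measured histologically on the prostatectomy specimen resected one month after TMA, compared to post TMA dimensions" on that scan. The second is the difference between histologic dimensions and the charts ("the predictive ablation charts provided by the manufacturer will be performed"), with the rule "For this analysis, the data from immediate resection phase and delayed resection phase are separately evaluated".

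The histologic reading in these men is on H&E only. Section 1.3 states "In this setting, we evaluate the ablation effect on histology using HE staining instead of TTC staining", and a footnote to the study calendar for the following ten patients confirms that no TTC is done. Section 6.0 has the gland cut at 4 mm intervals, each slice embedded, and the slides read by a pathologist to determine the size of the thermal zone. Section 9.1, on histology and MRI, repeats the text of Section 5.3.4: gross measurement, then "Digitally photographing of these sections will be done", and later "Routine tissue processing and H&E staining will be performed".

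Section 2.5 words both endpoints as correlations. Section 10.7 words them as comparisons and, for the charts, as a difference.

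Shrinkage is mentioned once, in Section 1.3. There it means fibrotic shrinkage in the body, and it is used to justify early resection.

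**The concern.** MRI measures the zone in the living gland. The H&E whole mount measures it after fixation, embedding and sectioning. If processing shrinks the tissue at all, the two measurements are on different scales, and the error always has the same sign: histology reads small and the predictor reads large. Section 1.3 says of biological shrinkage that it should be avoided "as these would invalidate accurate comparison between imaging versus histologic measurements". The same reasoning applies to shrinkage in the laboratory, which the plan does not address.

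What is at stake is the conclusion on two secondary objectives, the predictability of post-ablation mpMRI and of the ablation charts. An artefact of specimen handling could be reported as over-prediction by the scan or the device chart. With ten delayed patients, two per template, the data alone could not separate that artefact from a real error.

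**Working it through.** **1. Is there a correction anywhere?** Sections 5.3.4, 6.0, 9.1, 10.3 and 10.7 contain no shrinkage factor, no paired measurement before and after processing, and no rescaling. The photographs are not linked to any size measurement. The 3D-printed mold in Section 5.3.2 is for treatment planning. The plan states no figure of its own to reproduce: no shrinkage value, no agreement limit, and a sample size set by practical considerations.

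**2. Inputs from the documents.**
- Chart short × long axes (Section 4.2): 1.5 × 2.5, 2.0 × 2.7 and 2.5 × 3.0 cm, so the short axis rises in steps of 0.5 cm.
- MRI to prostatectomy (study calendar, footnote 2): 1 to 5 days, so little change in the body is expected between the two readings.
- Slice interval (Section 6.0): 4 mm.

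**3. Assumption.** Linear processing shrinkage s of 5% to 15%. This is not in the documents.

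**4. Effect on in-plane size.** The histologic length is the true length × (1 − s). A predictor that is exactly right therefore appears too large by 1/(1 − s) − 1 in length and by 1/(1 − s)² − 1 in area.

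| s | apparent excess, length | apparent excess, area | true 2.5 cm reads | loss as share of 0.5 cm step |
|---|---|---|---|---|
| 5% | 1/0.95 − 1 = 5.3% | 1/0.9025 − 1 = 10.8% | 2.375 cm | 0.125/0.5 = 25% |
| 10% | 1/0.90 − 1 = 11.1% | 1/0.81 − 1 = 23.5% | 2.250 cm | 0.250/0.5 = 50% |
| 15% | 1/0.85 − 1 = 17.6% | 1/0.7225 − 1 = 38.4% | 2.125 cm | 0.375/0.5 = 75% |

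At s = 0 every excess is zero. Dividing the H&E length by (1 − s) restores zero for any known s.

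**5. Effect on correlation.** Multiplying one variable by a positive constant leaves the Pearson coefficient unchanged: corr(x, ky) = corr(x, y) for k > 0. The correlation endpoint in Section 2.5 therefore does not move under constant shrinkage, and for the same reason it cannot reveal it.

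**6. The third axis.** Sections 5.3.4 and 9.1 describe serial transverse sectioning, and Section 6.0 has the slices embedded after cutting. If an extent is obtained by counting 4 mm slices cut before processing, it carries no embedding shrinkage. Applying an in-plane factor to it would add error: a correct 3.0 cm would become 3.0/0.95 = 3.16 cm to 3.0/0.85 = 3.53 cm. The documents do not say how this axis is measured.

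**The case against.** The strongest reply is that both endpoints are defined as correlations, which a constant factor does not touch, in an exploratory study of 15 men with no test or agreement limit on these dimensions. That stands for the correlation. It does not protect the comparison and difference in Section 10.7, which depend on scale.

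Four stronger readings are tempting, and the documents do not support them:
- **That the charts would be shown to over-predict overall.** Section 4.2 says the charts come from other soft tissues, and a month in the body also intervenes. Shrinkage pushes one way, but the net direction against the charts is not established.
- **That every dimension, and so volume, is biased.** A slice-counted axis may not shrink, and the planned measures are dimensions and area.
- **That a false difference between phases would be reported.** Section 10.7 evaluates the phases separately and plans no test between them. The split of TTC for one phase and H&E for the other is also partly inferred: Section 6.0 allows either or both stains, and Section 5.3.4 puts the first five specimens through H&E too.
- **That the primary endpoint is compromised.** It rests on TTC read macroscopically, which embedding shrinkage affects less. The proportion of dead tissue in Section 6.0 is a ratio, in which uniform shrinkage cancels.

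It is also fair to say that the plan does not state whether delayed glands are sliced and photographed fresh or fixed. If they are fixed first, a scaled photograph alone would miss shrinkage from fixation.

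**Conclusion.** The omission is confirmed, and the direction follows for any processing shrinkage above zero: in-plane difference or agreement comparisons in the delayed phase lean toward apparent over-prediction. The case is clearest for MRI. For the charts, processing shrinkage is one of several errors.

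The size is conditional. The figures in the table hold only under the assumed 5% to 15%, taken as uniform across the slice. At the upper end, the loss on a 2.5 cm zone is three quarters of the gap between adjacent charts, enough to change how a chart or scan is judged. The point concerns two secondary endpoints. It is worth correcting because the correction is cheap and cannot be made properly once the specimens have been processed without a reference size.

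**What to change.** In Sections 5.3.4 and 9.1, require a scale in the section photographs already planned, and record the gross gland width before fixation. State whether slicing is done on fresh or fixed tissue.

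In Sections 6.0 and 10.7:
- Define a per-patient linear factor: unprocessed width divided by the H&E width of the same slice or gland.
- Apply it to in-plane dimensions read on H&E, and its square to in-plane areas.
- Do not apply it to an axis obtained by counting 4 mm slices, and say how that axis is measured.
- Report corrected and uncorrected differences side by side, next to the correlation.

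The cost is a ruler in the photograph, one extra gross reading and one division per slice or gland. No patient procedure changes. It must be in place before the specimens are processed.

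The factor assumes that ablated and normal tissue shrink equally. It restores the size of the unprocessed specimen only, and does not remove chart error due to a month of change in the body or to charts derived from other tissues. Reporting both sets of values lets the reader see how much depends on the correction.
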